### 8.3. Safety criteria

The Principal Investigator and the GSK Medical Monitor will review the following and study dosing **will be** stopped if any of these criteria is met:

- One (1) or more participants experience a serious adverse event (SAE) which has a reasonable possibility of relation to study drug.
- Two (2) or more participants experience a severe or clinically significant non-serious adverse event (based upon investigator judgment) which has a reasonable possibility of relation to study drug.
- Two (2) or more participants in a Part A cohort or 3 or more participants in a Part B cohort experience the same adverse event of moderate severity which has a reasonable possibility of relation to study drug.
- Consistent Common Terminology Criteria for Adverse Events (CTCAE) Nervous System adverse events of any grade occur across participants that have a reasonable possibility of relation to study drug.

If dosing is halted and if deemed acceptable by GSK internal safety review to proceed with or modify dose escalation to further characterize the safety profile, a formal request with appropriate data and substantial amendment will be submitted to Medicines and Healthcare Products Regulatory Agency (MHRA) for approval.

## 9. DISCONTINUATION CRITERIA

### 9.1. Individual Safety Stopping Criteria

- If a participant experiences a serious or severe clinically significant AE that in the clinical judgement of the Investigator, after consultation with the Medical Monitor, is possibly, probably or definitely related to investigational product.
- The participant initiates treatment with any prohibited medications.
- The participant develops a serious opportunistic or atypical infection.
- If any of the liver chemistry stopping criteria or QTc stopping criteria are met.
- The participant experiences any signs of suicidal ideation or behaviour.

## 9.2. Neurological/psychiatric Stopping Criteria

The CNS observations in the first good laboratory practice (GLP) acute neurobehavioural study in rats were found to be present at all single doses. The same findings were not observed in a second study with overlapping doses. The CTCAE Nervous System is a monitoring tool which provides the Principal Investigator the appropriate guidance for grading of a neurological event. The significance of any neurological event experienced by a participant will be determined based on clinical judgment, characteristics of the event and/or based upon changes from a baseline assessment.

The Principal Investigator and the GSK Medical Monitor will review all neurological events utilizing the CTCAE Nervous System criteria

A participant **will be** withdrawn from the study if any of these criteria is met:

- A Grade 3 or greater CTCAE Nervous System finding (see SRM) is observed or a significant neurologic change from a participant's baseline physical examination is observed.
- Any adverse event included in the CTCAE for Nervous System, which is also considered to be clinically significant by the Principal Investigator, will be reviewed for potential participant withdrawal.

## 9.3. Liver Chemistry Stopping Criteria

[figure not shown]
**Liver chemistry stopping and increased monitoring criteria** have been designed to assure participant safety and evaluate liver event etiology (in alignment with the food and drug administration [FDA] premarketing clinical liver safety guidance). These protocol guidelines are in alignment with FDA premarketing clinical liver safety guidance:

<http://www.fda.gov/downloads/Drugs/GuidanceComplianceRegulatoryInformation/Guidances/UCM174090.pdf>.

Discontinuation of study treatment for abnormal liver tests should be considered by the investigator when a participant meets one of the conditions outlined in the algorithm or if the investigator believes that it is in the best interest of the participant.

Study treatment will be discontinued **for a participant** if liver chemistry stopping criteria are met:

## Phase I Liver Chemistry Stopping Criteria – Liver Stopping Event Algorithm

Liver Safety Required Actions and Follow up Assessments Section can be found in Section [13.6](#)

### 9.3.1. Study Treatment Restart or Rechallenge

During part B, study treatment restart or rechallenge after liver chemistry stopping criteria are met by any participant in this study is not allowed.

### 9.4. QTc Stopping Criteria

- The *same* QT correction formula *must* be used for *each individual participant* to determine eligibility for and discontinuation from the study. This formula may not be changed or substituted once the participant has been enrolled.
  - For example, if a participant is eligible for the protocol based on QTcB, then QTcB must be used for discontinuation of this individual participant as well.
  - Once the QT correction formula has been chosen for a participant's eligibility, the *same formula* must continue to be used for that participant *for all QTc data being collected for data analysis*. Safety ECGs and other non-protocol specified ECGs are an exception.
- The QTc should be based on single or averaged QTc values of triplicate electrocardiograms obtained over a brief (e.g., 5-10 minute) recording period.

A subject that meets either bulleted criterion based on the average of triplicate ECG readings will be withdrawn from study treatment.

- QTc > 500 msec,
- Change from baseline: QTc >60 msec increase

See the SoA for data to be collected at the time of treatment discontinuation and follow-up and for any further evaluations that need to be completed.

### **9.5. Withdrawal from the Study**

- A participant may withdraw from the study at any time at his/her own request, or may be withdrawn at any time at the discretion of the investigator for safety, behavioral, compliance or administrative reasons.
- If the participant withdraws consent for disclosure of future information, the sponsor may retain and continue to use any data collected before such a withdrawal of consent.
- If a participant withdraws from the study, he/she may request destruction of any samples taken and not tested, and the investigator must document this in the site study records.
- Refer to the SoA for data to be collected at the time of study discontinuation and follow-up and for any further evaluations that need to be completed.

### **9.6. Lost to Follow Up**

A participant will be considered lost to follow-up if he or she repeatedly fails to return for scheduled visits and is unable to be contacted by the study site.

The following actions must be taken if a participant fails to return to the clinic for a required study visit:

- The site must attempt to contact the participant and reschedule the missed visit as soon as possible and counsel the participant on the importance of maintaining the assigned visit schedule and ascertain whether or not the participant wishes to and/or should continue in the study.
- Before a participant is deemed lost to follow up, the investigator or designee must make every effort to regain contact with the participant (where possible, 3 telephone calls and, if necessary, a certified letter to the participant's last known mailing address or local equivalent methods). These contact attempts should be documented in the participant's medical record.
- Should the participant continue to be unreachable, he/she will be considered to have withdrawn from the study with a primary reason of lost to follow-up.

## **10. STUDY ASSESSMENTS AND PROCEDURES**

- Study procedures and their timing are summarized in the SoA.
- Protocol waivers or exemptions are not allowed

- Immediate safety concerns should be discussed with the sponsor immediately upon occurrence or awareness to determine if the participant should continue or discontinue study treatment.
- Adherence to the study design requirements, including those specified in the SoA, is essential and required for study conduct.
- All screening evaluations must be completed and reviewed to confirm that potential participants meet all eligibility criteria. The investigator will maintain a screening log to record details of all participants screened and to confirm eligibility or record reasons for screening failure, as applicable.
- Procedures conducted as part of the participant's routine clinical management (eg, blood count) and obtained before signing of ICF may be utilized for screening or baseline purposes provided the procedure met the protocol-specified criteria and was performed within the time frame defined in the SoA.
- The maximum amount of blood collected from each participant over the duration of the study, including any extra assessments that may be required, will not exceed 500 mL.
- Repeat or unscheduled samples may be taken for safety reasons or for technical issues with the samples.

## **10.1. Adverse Events**

The definitions of an AE or SAE can be found in [Appendix 4](#).

The investigator and any designees are responsible for detecting, documenting, and reporting events that meet the definition of an AE or SAE and remain responsible for following up AEs that are serious, considered related to the study treatment or the study, or that caused the participant to discontinue the study (see Section 9).

### **10.1.1. Time Period and Frequency for Collecting AE and SAE Information**

- All SAEs will be collected from the start of treatment until the follow-up visit at the time points specified in the SoA (Section 2). However, any SAEs assessed as related to study participation (e.g., study treatment, protocol-mandated procedures, invasive tests, or change in existing therapy) or related to a GSK product will be recorded from the time a subject consents to participate in the study.
- All AEs will be collected from the start of treatment until the follow-up visit at the time points specified in the SoA (Section 2).
- Medical occurrences that begin before the start of study treatment but after obtaining informed consent will be recorded on the Medical History/Current Medical Conditions section of the case report form (CRF) not the AE section.
- All SAEs will be recorded and reported to the sponsor or designee within 24 hours after becoming aware of the event, as indicated in [Appendix 4](#). The

investigator will submit any updated SAE data to the sponsor within 24 hours of it being available.

- Investigators are not obligated to actively seek AEs or SAEs in former study participants. However, if the investigator learns of any SAE, including a death, at any time after a participant has been discharged from the study, and he/she considers the event to be reasonably related to the study treatment or study participation, the investigator must promptly notify the sponsor.
- The method of recording, evaluating, and assessing causality of AEs and SAEs and the procedures for completing and transmitting SAE reports are provided in [Appendix 4](#).

#### **10.1.2. Method of Detecting AEs and SAEs**

Care will be taken not to introduce bias when detecting AE and/or SAE. Open-ended and non-leading verbal questioning of the participant is the preferred method to inquire about AE occurrence.

#### **10.1.3. Follow-up of AEs and SAEs**

After the initial AE/SAE report, the investigator is required to proactively follow each participant at subsequent visits/contacts. All SAEs, will be followed until the event is resolved, stabilized, otherwise explained, or the participant is lost to follow-up (as defined in Section 9.6). Further information on follow-up procedures is given in [Appendix 4](#).

#### **10.1.4. Regulatory Reporting Requirements for SAEs**

- Prompt notification by the investigator to the sponsor of a SAE is essential so that legal obligations and ethical responsibilities towards the safety of participants and the safety of a study treatment under clinical investigation are met.
- The sponsor has a legal responsibility to notify both the local regulatory authority and other regulatory agencies about the safety of a study treatment under clinical investigation. The sponsor will comply with country-specific regulatory requirements relating to safety reporting to the regulatory authority, Institutional Review Boards (IRB)/Independent Ethics Committees (IEC), and investigators.
- Investigator safety reports must be prepared for suspected unexpected serious adverse reactions (SUSAR) according to local regulatory requirements and sponsor policy and forwarded to investigators as necessary.
- An investigator who receives an investigator safety report describing a SAE or other specific safety information (e.g., summary or listing of SAE) from the sponsor will review and then file it along with the Investigator's Brochure and will notify the institutional review board/independent ethics committee (IRB/IEC), if appropriate according to local requirements.

### **10.1.5. Pregnancy**

- Details of all pregnancies in female partners of male participants will be collected after the start of study treatment and until 30 days after the last dose.
- If a pregnancy is reported, the investigator should inform GSK within 24 hours of learning of the pregnancy and should follow the procedures outlined in Section 13.5.
- Abnormal pregnancy outcomes (e.g., spontaneous abortion, fetal death, stillbirth, congenital anomalies, ectopic pregnancy) are considered SAE.

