Reproductive toxicity	
Non-clinical data:
 
Animal reproductive studies have not been conducted with GSK2983559. Therefore, the compound must not be administered to pregnant women, nursing mothers or women of childbearing potential.
	
Subject Selection:
 
 
Male and female participants of non-childbearing potential (WONCBP) may be included in this study.
 
Male participants must agree to use highly effective methods of contraception during the treatment period and for at least 5 half-lives plus an additional 90 days after the last dose of study treatment and refrain from donating sperm during this period (Appendix 5).
 

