### **Treatment period**

- Cohort 1 (single dose) will be comprised of up to 5 study periods, each at least 4 days in duration with participants in-house for 3 nights (through 48 hours post-dose). During each treatment period, participants will be admitted to the unit the day before dosing and will be discharged after completion of the 48-hour post-dose assessments.
- Cohort 2 (single dose) will be comprised of up to 4 study periods, each at least 4 days in duration with participants in-house for 3 nights (through 48 hours post-dose). During each treatment period, participants will be admitted to the unit the day before dosing and will be discharged after completion of the 48-hour post-dose assessments.
- Participants in Cohort 2 (food effect) will participate in up to 2 additional treatment periods and receive a single oral dose of GSK2983559 under fasted (Period 4) and/or fed (Period 5) conditions, dose to be determined by DEC.

If the dose level chosen for the food effect assessment was administered in:

- Cohort 1: participants will receive the dose of open-label GSK2983559 under fasted (Period 4) and fed (Period 5).
- Cohort 2: participants will only receive the dose of open-label GSK2983559 under fed (Period 5) conditions.
- All participants will participate in no more than 5 Treatment Periods (see [Table 5](#) and [Table 6](#)).
- Participants will have a follow-up visit at least 7 days or 5 half-lives whichever is longer, and no greater than 14 days after last dose of GSK2983559. If warranted, additional follow-up visits may be scheduled.

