### **5.3. Participant and Study Completion**

A participant is considered to have completed:

- Part A (cohort 1) of the study if he/she has completed all the periods of Part A – cohort 1, including the follow-up visit.
- Part A (cohort 2 – single dose) of the study if he/she has completed all the periods of Part A – cohort 2 – single dose, including the follow-up visit.
- Part A (cohort 2 – food effect) of the study if he/she has completed the 2 periods of Part A – cohort 2 – food effect, including the follow-up visit.
- Part B of the study if he/she has completed all visits including the follow-up visit.

The end of the study is defined as the date of the last visit (including follow-up) of the last participant in the study (Part A and Part B).

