## 6.1. Inclusion Criteria

AGE	
1.	Male and female participants between 18 and 65 years of age inclusive, at the time of signing the informed consent.
TYPE OF PARTICIPANT AND DISEASE CHARACTERISTICS	
2.	Volunteers who are overtly healthy as determined by medical evaluation including medical and psychiatric history, physical examination, neurological examination, clinical laboratory tests and cardiac monitoring.
WEIGHT	
3.	Body weight $\geq$ 50 kg and body mass index (BMI) within the range 19-32 kg/m  (inclusive).
SEX	
4.	
Male and female participants:
 
a. Male participants:
 
A male participant must agree to use a highly effective contraception (see below) during the treatment period and for at least 5 half-lives plus an additional 90 days after the last dose of study treatment and refrain from donating sperm during this period.
 
 
• Male participants with female partners of child-bearing potential are eligible to participate if they agree to ONE of the following during the protocol-defined time frame above: 
 
• Are abstinent from penile-vaginal intercourse as their usual and preferred lifestyle (abstinent on a long term and persistent basis) and agree to remain abstinent
 
• Agree to use a male condom plus an additional method of contraception with a failure rate of <1% per year as described in Appendix 5 when having penile-vaginal intercourse with a woman of childbearing potential
 
 
 
• Men with a pregnant or breastfeeding partner must agree to remain abstinent from penile-vaginal intercourse or use a male condom during each episode of penile penetration during the protocol-defined time frame.
 
• Refrain from donating sperm for duration of study and for 90 days from the last dose.
 
 
b. Female participants:
 
A female participant is eligible to participate if she is not pregnant (see Appendix 5), not breastfeeding, and is not a woman of childbearing potential (WOCBP) as defined in Appendix 5.

INFORMED CONSENT	
5.	Capable of giving signed informed consent which includes compliance with the requirements and restrictions listed in the informed consent form (ICF) and in this

protocol.

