## **Collection of Pregnancy Information**

### **Male participants with partners who become pregnant**

- Investigator will attempt to collect pregnancy information on any male participant's female partner of a male study participant who becomes pregnant while participating in this study. This applies only to participants who receive study treatment.
- After obtaining the necessary signed informed consent from the pregnant female partner directly, the investigator will record pregnancy information on the appropriate form and submit it to GSK within 24 hours of learning of the partner's pregnancy.
- Partner will also be followed to determine the outcome of the pregnancy. Information on the status of the mother and child will be forwarded to GSK.
- Generally, follow-up will be no longer than 6 to 8 weeks following the estimated delivery date. Any termination of the pregnancy will be reported regardless of fetal status (presence or absence of anomalies) or indication for procedure.

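### Partner pregnancies are collected only to 30 days after the last dose, about 61 to 62 days short of the protocol's own male contraception period (low priority)

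*Protocol*

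**What the plan says.** Three parts of the protocol bear on this point.

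- **Risk period.** The reproductive-toxicity row of Section 3.3.1 gives the reason for the precaution: "Animal reproductive studies have not been conducted with GSK2983559". As mitigation, that row and criterion 4a in Section 6.1 oblige men to use contraception and not to donate sperm during treatment and "for at least 5 half-lives plus an additional 90 days after the last dose of study treatment". The contraception guidance in Appendix 5 (Section 13.5) refers back to the Section 6.1 time frame.
- **Collection period.** Section 10.1.5 states that details of partner pregnancies "will be collected after the start of study treatment and until 30 days after the last dose".
- **Other reporting routes.** The second bullet of Section 10.1.5 has no time limit: "If a pregnancy is reported, the investigator should inform GSK within 24 hours of learning of the pregnancy". It sends the reader to Section 13.5 for the procedure, and collection there concerns a partner "who becomes pregnant while participating in this study". The third bullet classes abnormal pregnancy outcomes as serious adverse events. Under Section 10.1.1, "if the investigator learns of any SAE, including a death, at any time after a participant has been discharged from the study" and considers it reasonably related to the treatment or to participation, the sponsor must be told promptly. The same section says investigators need not actively look for events in former participants.

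**The concern.** The contraception period is the sponsor's own statement of how long a conception might be affected by the drug. The collection window shows when the sponsor expects to hear about conceptions. Here the second stops about one third of the way through the post-dose part of the first.

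At stake is a small amount of safety information that is hard to replace. The compound is new to humans and has no animal reproductive data. Its impurity and acid degradant 5-ABT is mutagenic in an Ames assay (Section 3.3.1) and was quantifiable in plasma in 4 of 8 participants given active drug at 100 mg (Section 5.5.5). A contraceptive failure between about day 30 and day 91 is an event the precaution was meant to prevent, yet a site following Section 10.1.5 to the letter would not be asking about it.

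**Working it through.** There is no plan figure to reproduce. The check is day arithmetic, followed by a reading of the other reporting routes.

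**Inputs**

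- End of collection: day 30 after the last dose (Section 10.1.5).
- End of contraception: 5 half-lives plus 90 days after the last dose, as a minimum (Sections 3.3.1 and 6.1).
- Half-life: 4.6 h predicted (Section 5.5.1), 5 h estimated (Section 5.4), about 8 h observed for the active moiety (Section 5.5.4, dose selection for Part B).

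**Formulas**

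- End of contraception (days) = 90 + 5 × half-life (h) / 24
- Gap (days) = end of contraception − 30
- Share = gap / end of contraception

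| Half-life | 5 half-lives | End of contraception | Gap | Share of post-dose period |
|---|---|---|---|---|
| 4.6 h | 23 h = 0.96 d | day 90.96 | 60.96 d | 67.0% |
| 5 h | 25 h = 1.04 d | day 91.04 | 61.04 d | 67.0% |
| 8 h | 40 h = 1.67 d | day 91.67 | 61.67 d | 67.3% |

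The choice of half-life hardly matters, because the fixed 90 days dominate. The gap is a minimum, since the contraception rule sets a lower limit. The separate sperm-donation bullet in Section 6.1, which gives 90 days alone, still leaves 90 − 30 = 60 days.

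**Does another route close the gap?**

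- The open-ended second bullet of Section 10.1.5 says what to do once a report arrives. It does not ask men to make one after day 30.
- Appendix 5 ties collection to participation in the study and does not extend the window.
- Section 10.1.1 covers only serious events that the investigator happens to learn of and judges related. An ongoing or normal pregnancy does not fall under it.

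**A second ambiguity.** Section 10.1.5 does not say whether day 30 refers to conception, recognition or reporting. A pregnancy conceived inside the window but recognised afterwards could be missed, and moving the end date alone would carry the same problem to day 91.

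**Illustration only.** Assume that all 22 planned Part A participants are men with a partner of childbearing potential, that contraception fails at 1% per year, and that condoms add nothing. The expected number of pregnancies in the gap is then 22 × 0.01 × 61.67 / 365 = 0.04. Typical-use failure would raise this; condom use and female participants would lower it. None of these assumptions comes from study data.

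**The case against.** The strongest reply is that nothing is in error. Section 6.1 governs what participants do and Section 10.1.5 governs what the site collects, and no text in either document says the two periods must match. That stands: a reader might infer a contradiction, but the documents do not contain one.

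A second reply is that later pregnancies are not shut out. This also stands in part. The second bullet of Section 10.1.5 can be read to cover any report that reaches the site, and related serious outcomes can arrive through Section 10.1.1. It would be too strong to say that pregnancies after day 30 go unreported. What is missing is any request for them.

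A third reply is that an instruction to men would naturally sit in the consent form. Those pages were not available for review, so nothing can be concluded about them, and the point is limited to the visible protocol text.

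A reader might also infer that Appendix 5 sets an even shorter window. Section 5.3 says a participant has completed "Part B of the study if he/she has completed all visits including the follow-up visit", with matching rules for Part A, and the follow-up visit is "no greater than 14 days after last dose of GSK2983559", so participation might be taken to end by day 14. The documents do not support this firmly. Section 5.3 defines completion, not what participating means for pregnancy collection, and the more natural reading is that Section 10.1.5 sets the time and Appendix 5 the steps.

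**Conclusion.** The point holds as a low-priority misalignment. The stated collection window leaves out about 61 to 62 days, roughly two thirds, of the post-dose period in which the protocol itself asks men to prevent conception. That figure rests only on protocol numbers and holds for every half-life given.

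The practical weight is small. Few events would be expected. The SAP (Sections 2.1 and 2.3) records that the study was terminated during Cohort 2 of Part A and that Part B never started. No endpoint, dose-escalation rule or planned analysis is affected. The value of a correction now lies mainly in any later protocol for this compound that reuses the wording.

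**What to change.** - **Section 10.1.5:** collect details of every partner pregnancy whose estimated conception date falls between the start of study treatment and the end of the male contraception period (no less than 5 half-lives plus 90 days beyond the final dose), whenever it is recognised or reported. Tying the rule to conception date matters; otherwise a conception late in the period would still be missed.
- **Appendix 5:** replace the reference to participating in the study with the same period, so that the rule and its procedure share one window.
- **Participants:** remind men at discharge and at the follow-up visit to report any such pregnancy, and align the consent form if it carries the shorter period.

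The cost is wording in two sections and a reminder at two existing contacts, with no added visit or test. The downside is about two more months of passive reporting for site and participants.
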